##### **Visit 3 (Day 30+/-3)**

The following surveys will be administered for visit three:

*Surveys administered to the PWD are indicated by their QDRS score:*

- PAINAD (If QDRS >12)
- FAM-CAM
- BPI (If QDRS≤12)
- NPI-Q
- Katz ADLs and Lawton iADLS (through the QOL-AD)
- Resource Utilization Inventory
- Non-instrumented: Medication Record and Usage, Resource Utilization Inventory, AE and SAE, COVID-19 questions

### 7.2.5 Final Study Visit

#### **Final Study Visit (Visit 4, Day 60+5)**

The following surveys will be administered for visit four:

*Surveys administered to the PWD are indicated by their QDRS score:*

- PAINAD (If QDRS >12)
- FAM-CAM
- BPI (If QDRS≤12)
- QOL-AD (If QDRS≤12)
- NPI-Q
- CGQOL:
- Public Health Questionnaire 9 (PHQ-9)
- Zarit Burden Inventory
- SF-12
- Charlson Comorbidity
- Resource Utilization Inventory

CONFIDENTIAL

This material is the property of the NYU School of Medicine and Langone Medical Center. Do not disclose or use except as authorized in writing by the study sponsor

- HHCAHPS
- Katz ADLs and Lawton IADLS (through the QOL-AD)
- Non-instrumented: Medication Record and Usage, Resource Utilization Inventory, AE and SAE
- Information obtained from the chart includes: Number of visits by the home healthcare staff by type, comorbidities, COVID-19 questions.

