## 3 Objectives and Purpose

### 3.1 Primary Objectives

***Aim 1: Measure the effects of the DSM-H on quality of life and symptom severity in the PWD.***

H1: PWD cared for by a HHC team utilizing the DSM-H performance improvement program will show reduced symptoms and improved ratings of pain, BPSD, and caregiver-rated QOL at the end of the first 60-day HHC certification period compared to the control (usual care) group.

The primary outcome of Aim 1 is caregiver rated QOL. It will be measured using the Quality of Life-Alzheimer's Disease.

***Aim 2: Assess the effects of the DSM-H on quality of life, and physical and mental health in the informal caregiver of the PWD.***

H2: Informal caregivers of PWD cared for by a HHC team utilizing the DSM-H performance improvement program will show reduced ratings of burden, and depression, and improved functional health and well-being at the end of the first 60-day HHC certification period compared to the control (usual care) group.

The primary outcome of Aim 2 is informal caregiver QOL. It will be measured using the Caregiver-Targeted Quality of Life Measure.

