## 7.2 Study Schedule

### 7.2.1 Screening

Screening is initiated during the initial call and completed prior to subjects being introduced to the informed consent process.

The research team will contact patients and caregivers who have “not opted out” from being contacted based on their HHC agency’s referral. The research team will inquire on their interest in learning about the study and whether they may be interested in participating prior to screening for eligibility. Screening will be initiated in the first contact to ensure that they have met the inclusion/exclusion criteria. To determine if the PWD’s level of cognitive impairment meets eligibility for inclusion, the QDRS will be administered to the caregiver who will rate the PWD’s symptoms and behaviors. Caregivers will be provided with a copy of the QDRS assessment form for their review. A research team member will complete the form with the caregiver over the phone. A score will be tallied to determine the PWD’s level of cognitive impairment. A PWD who obtains a score  $\geq 6$  on the QDRS will meet eligibility for study inclusion. If the screening is positive and the PWD and caregiver are interested in participating, the research team member will conduct the informed consent process. The screening, informed consent, and visit one assessments for each subject will be completed within 3 business days from the PWD’s start of care date. In circumstances where subjects who provide their consent verbally yet lack the ability to electronically sign the informed consent document due to lack of internet access or computer literacy, we will mail them a copy of the consent form to review and confirm at visit 2 their intent to continue participation in order to ensure equity in participation. Providing consent/assent has been obtained, the remainder of the virtual visit will be utilized for subject data collection. Further, the QDRS score will determine which assessments are administered to the PWD.

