#### Enrollment/Baseline Visit

**Visit 1, (Day 0/1)** the following surveys will be collected during visit one. Surveys administered to the PWD are indicated by their QDRS score:

- PAINAD (if QDRS>12)
- FAM-CAM
- Brief Pain Inventory Short Form (BPI; if QDRS $\leq 12$ ).
- Quality of Life in Alzheimer’s Disease (QOL-AD) (if QDRS  $\leq 12$ )
- Neuropsychiatric Inventory Questionnaire (NPI-Q)
- Caregiver Targeted Quality of Life Tool (CGQOL):
- Public Health Questionnaire 9 (PHQ-9)
- Zarit Burden Inventory
- SF-12
- Charlson Comorbidity

CONFIDENTIAL

This material is the property of the NYU School of Medicine and Langone Medical Center. Do not disclose or use except as authorized in writing by the study sponsor

- Katz ADLs and Lawton iADLS (through the QOL-AD)
- The Short Assessment of Health Literacy (SAHL)
- Other non-instrumented questions that will be asked include sociodemographics (DOB, sex, highest education level attained, race, ethnicity, primary language, religion, marital status, household members, number type and frequency of unpaid and paid caregivers, medication record and use, primary care provider name and contact for both PWD and caregiver).
- Information obtained from the chart includes: Number of visits by the home healthcare staff by type, comorbidities, COVID-19 questions.

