### **10.2 Statistical Hypotheses**

H1: PWD cared for by a HHC team utilizing the DSM-H will show reduced symptoms and improved ratings of pain, BPSD, and caregiver-rated QOL at the end of the first 60-day HHC certification period compared to the control (usual care) group.

H2: Informal caregivers of PWD cared for by a HHC team utilizing the DSM-H will show reduced ratings of burden, and depression, and improved functional health and well-being at the end of the first 60-day HHC certification period compared to the control (usual care) group.

H3: PWD cared for by a HHC team utilizing the DSM-H will show a reduction in emergency room visits and hospital admissions compared to the control (usual care) group, and a greater number of outpatient visits.

CONFIDENTIAL

This material is the property of the NYU School of Medicine and Langone Medical Center. Do not disclose or use except as authorized in writing by the study sponsor

Interventional Template Version: 28 APR 2017

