## 10.5 Sample Size

Power analyses were conducted using Optimal Design software. Given that this study is randomized at the cluster level, we must control for intra-class correlation, and have therefore calculated all power with an intra-class coefficient of .05, which is more conservative than the most recent clustered palliative care study and aligns well with prior community-based cluster trials. The Quality of Life in Alzheimer's Disease as the primary outcome measure in aim 1 has an average score of 33.1, standard deviation of 5.9. A .5 standard deviation difference in this measure would be clinically meaningful. Therefore, in a 2-sample comparison with a power of .80, an alpha of .05 and covariates that account for a cumulative 15% of the variance in outcome would require 15 dyads per cluster, and 20 clusters (10 per arm) at 60 days to detect a medium effect ( $\delta = .45$ ). For mixed effects linear models, the projected sample size will also allow us to detect a medium linear treatment effect ( $\delta = .45$ ) between groups in unadjusted analyses (assuming 15 dyads per cluster, 20 clusters, 4 observations, and an ICC = .05). Although there are no closed-form equations for calculating the power of linear models that include covariates, any non-zero correlation between covariates and the outcome will reduce the unexplained (error) variance thus increasing the statistical power of our tests, and reducing the minimum detectable effect size. As such, the detectable effect size estimated for the unadjusted analyses can be considered an upper bound estimate for the effect size detectable in adjusted analyses. **We will recruit until we have reached 15 completed cases in each cluster (N=300).** Conservatively anticipating a 15% dropout over the 60 days requires a **total recruitment goal of 345 dyads**. As almost 20,000 patients are seen each year in the three HHC agencies in this study, approximately 30% with ADRD, we do not expect any difficulty recruiting this sample, even with an unanticipatedly high rate of dyads declining to participate.

In addition, for fidelity monitoring, as discussed in section [6.1.6.1](#), we will consent **300 clinicians** at the participating HHC agencies on usual care and quality improvement care teams to complete fidelity monitor by performing the DSKA survey. These clinicians are not study subjects but will be consented as they are

CONFIDENTIAL

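### The visit schedule gives the QOL-AD only when QDRS is 12 or below, so it does not schedule the caregiver-rated Aim 1 primary outcome for all eligible dyads

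*Combined protocol and SAP*

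**What the plan says.** **The outcome and its rater.** Section 3.1 states: "The primary outcome of Aim 1 is caregiver rated QOL", with the QOL-AD as the instrument. H1 in section 10.2 predicts "improved ratings of pain, BPSD, and caregiver-rated QOL at the end of the first 60-day HHC certification period". Section 7.1.1 describes the QOL-AD as a measure of the caregiver's perception. Table 2 ticks it for the caregiver at days 0 and 60 and has no patient tick. None of these places sets a QDRS limit.

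**The population and the sample size.** Section 5.1 admits a QDRS of 6 or more with no upper bound. Section 10.5 describes the QOL-AD "as the primary outcome measure in aim 1 has an average score of 33.1, standard deviation of 5.9", and adds: "We will recruit until we have reached 15 completed cases in each cluster", for a total of 300.

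**The visit lists.** Only 7.2.2 (baseline) and 7.2.5 (day 60) schedule the QOL-AD as an instrument. The baseline entry, "Disease (QOL-AD) (if QDRS", continues with a limit of 12 or below. The day-60 entry is "QOL-AD (If QDRS≤12". Neither list has a second, unconditional QOL-AD line. The same lists carry other caregiver instruments without a condition, for example "Caregiver Targeted Quality of Life Tool (CGQOL", the PHQ-9, the Zarit and the SF-12. Section 7.2.1 explains the limit: "the QDRS score will determine which assessments are administered to the PWD".

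**The concern.** Staff working from the section 7.2 lists are told to give the QOL-AD only when the QDRS is 12 or below, although dyads above 12 are eligible and count towards recruitment. Nothing in 3.1, 10.2 or 10.5 confines Aim 1 to milder dementia.

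Two things are at stake. The first is the question answered: if the lists are applied as written, Aim 1 describes only people with a QDRS of 12 or below. The second is data that cannot be recovered. Section 4.2.1 judges Aim 1 on baseline and 60-day QOL, and a rating not taken at those visits cannot be obtained later.

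The completion rules do not catch the gap. Section 10.5 does not define a completed case, and 5.4 terminates subjects only if the caregiver does not complete visit four. A dyad above 12 could therefore count as complete with no primary-outcome value.

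**Working it through.** **1. The passages side by side**

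| Place | Rater | QDRS condition |
|---|---|---|
| 3.1, 10.2 (H1), 7.1.1 | Caregiver | None |
| 10.5 | Not stated | None; all 300 completers assumed |
| Table 2, days 0 and 60 | Caregiver only | None shown |
| 7.2.2, Visit 1 list | Not stated | 12 or below |
| 7.2.5, Visit 4 list | Not stated | 12 or below |

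Table 2 is evidence for rater and timing only. It shows no QDRS condition for any instrument, including the pain tools that 3.2 does split by QDRS, so its silence does not prove that the QOL-AD limit was unintended.

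**2. The two readings of the limit**

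- *It applies to the QOL-AD as such.* The caregiver rating is then not taken above 12, contrary to 3.1 and 5.1.
- *It applies only to a QOL-AD given to the person with dementia.* No section describes a self-rated version, and Table 2 has no patient tick for one. The lists then contain no caregiver QOL-AD line at all.

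Neither reading schedules the primary outcome for every eligible dyad.

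**3. The plan's own power figure**

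Inputs from 10.5: 20 clusters (J), 15 dyads per cluster (m), ICC 0.05, alpha 0.05 (taken as two-sided), effect 0.45 SD. No covariates are used.

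- Variance of the standardized difference = 4 × (ICC + (1 − ICC)/m)/J
- Noncentrality = 0.45/√variance, with a t distribution on J − 2 = 18 degrees of freedom
- m = 15: 4 × (0.05 + 0.95/15)/20 = 0.02267; noncentrality 0.45/0.1506 = 2.99; power **0.807**; detectable effect 0.446 SD

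This reproduces the stated 0.80, and it needs a QOL-AD from all 300.

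**4. If the lists are followed literally**

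Let f be the share of completers with a QDRS above 12. The documents do not give f, so a range is shown. Assume that dyads above 12 count as completed and are not replaced, that every cluster loses the same share, and that the SD does not change. Then m = 15 × (1 − f).

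| f (assumed) | m | Dyads with QOL-AD | Variance | Noncentrality | Power at 0.45 SD | Detectable effect (SD) |
|---|---|---|---|---|---|---|
| 0 | 15 | 300 | 0.02267 | 2.99 | 0.807 | 0.446 |
| 0.2 | 12 | 240 | 0.02583 | 2.80 | 0.754 | 0.476 |
| 0.3 | 10.5 | 210 | 0.02810 | 2.68 | 0.719 | 0.497 |
| 0.5 | 7.5 | 150 | 0.03533 | 2.39 | 0.620 | 0.557 |

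Letting the loss vary binomially between clusters (4,000 draws, inverse-variance cluster weights) gives a mean power of 0.715 at f = 0.3 and 0.613 at f = 0.5.

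**5. Other bases for the same calculation**

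| Basis | f = 0 | f = 0.3 | f = 0.5 |
|---|---|---|---|
| Unadjusted, 0.45 SD | 0.807 | 0.719 | 0.620 |
| 15% of variance explained at both levels, 0.45 SD | 0.865 | 0.786 | 0.690 |
| Unadjusted, 0.50 SD | 0.881 | 0.805 | 0.711 |

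**The case against.** The strongest reply is that the limit was never meant for the caregiver. Sections 7.2.1 and 7.2.5 speak of assessments given to the person with dementia. The other limited tools, the BPI and PAINAD, sit in Table 2's patient columns, while caregiver-reported tools are unconditional in the lists. On that pattern the limited line is a self-rating, and the caregiver line was simply left off two lists, with Table 2 supplying it. This is the more natural reading, and it makes the harmful outcome less likely. It does not remove the error: the self-rating is undescribed, and the lists still lack the primary outcome.

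Both lists also carry an unconditional line for the Katz and Lawton items, taken through the QOL-AD, which suggests that some part of that form is used at every QDRS level. Those are functional-status items, 12 in number, in a separate Table 2 row from the 13-item QOL-AD. They are also listed at Visits 2 and 3, where Table 2 schedules no QOL-AD. The line does not fill the gap.

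Section 5.6 aims for 300 evaluable dyads, and a dyad with no QOL-AD is not naturally evaluable for Aim 1. If such dyads were replaced, power would hold. That is a fair limit on the power argument, but the term is undefined, and replacement would still restrict Aim 1 to milder dementia.

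The power loss also depends on the basis chosen. At f = 0.3, covariate adjustment or a 0.50 SD effect leaves power at about 0.79 or 0.81 instead of 0.72. That stands.

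Finally, the Study Manual and the dyad instruments may settle the matter in practice. They were not available for this review. Section 18 places them outside the protocol and lets them change without an amendment, and 10.1 says no formal SAP will be written, so the protocol text has to be right by itself.

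**Conclusion.** The concern holds. The section 7.2 visit lists contradict 3.1, 7.1.1, 10.2 and Table 2 on the Aim 1 primary outcome, and under either reading they do not schedule it for all eligible dyads. The caregiver QOL-AD is not absent from the protocol, since Table 2 schedules it; the fault is confined to the two lists.

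The mismatch is certain and the consequence is conditional. If caregivers are rated at every QDRS level, nothing is lost. If the lists are followed literally, Aim 1 is limited to people with a QDRS of 12 or below. If those above 12 are also not replaced, unadjusted power at 0.45 SD falls from 0.81 to about 0.72 (30% above 12) or 0.62 (50% above 12). Both shares are assumptions. The correction is needed because a primary outcome is affected and missed ratings cannot be recovered.

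**What to change.** In 7.2.2 and 7.2.5, replace the limited entry with a line such as: QOL-AD, caregiver-rated, all dyads at any QDRS score. This matches 3.1 and the caregiver columns of Table 2 at days 0 and 60.

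If a self-rated QOL-AD is wanted for people with a QDRS of 12 or below, give it its own line in both lists and in Table 2, label it non-primary, and do not pool it with the caregiver score.

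The cost is a wording amendment to two lists, plus a Table 2 row if a self-rated version is kept. The caregiver rating adds no burden beyond the 5 minutes Table 2 already allots at each of the two visits.

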### 7.2.6 Collection of Home Health Record

Following the final study visit, the home health agency will extract the PWD subject's health record, including OASIS documentation, symptom scores, assessment information, and administrative visit information.

### 7.2.7 Withdrawal/Early Termination Visit

Should individuals withdraw from the study for any reason, we will attempt to ask for the reason and ask if any SAE or AE have occurred if the PWD/caregiver are reachable. We will also if withdrawal is for non-communication with the study team we will review the HHC medical record to ascertain if there was an SAE or AE.

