The legal surrogate will be verified by either the HHC agency or through written documentation. Should they not have written documentation of being an appointed surrogate, the law of the state of residence will determine the priority order for determining the surrogate, which is as follows:

Florida: spouse, adult child, parent, adult sibling, close friend

New Jersey: spouse, adult child, parent, sibling, close friend

Utah: spouse, adult child, parent, sibling, grandchild, grandparent, individual who is healthcare proxy

Because PWD in HHC are primarily homebound, tend to receive HHC for at least 60 days, with follow-up is provided through scheduled home visits, we do not anticipate significant retention problems. Additionally, the study burden is minimal, requiring approximately an hour per dyad at baseline and 60-days, and 20 minutes at the 15 and 30 days. Study staff will obtain detailed contact information for the PWD, caregiver, and where applicable proxy, will schedule the follow-up visits at the initial visit, email or text the visit schedule to the caregiver (based on caregiver preference; no PHI or PII included, see templates), and call 4 days and 1 day prior to each follow-up appointment to confirm and/or reschedule.

The greatest risks to retention are re-hospitalization and institutionalization, either for short-term post-acute rehabilitation after a re-hospitalization or long-term institutionalization for ADRD. Subjects are not required to attend the intermediate and final visits together. Efforts to accommodate the subjects' schedules will be considered in data collection. Phone interviews with the PWD and caregiver to collect participant survey data will occur for all time points. If both subjects are unavailable to complete an intermediate visit, the visit will be recorded as missed. To maintain subject retention, subjects will be terminated from the study only if the caregiver, as respondent, does not complete visit four.

Dyads will be enrolled starting in month 6 of year 1 and continuing through month 9 of year 4 (3 years, 3 months). Follow-up will continue through Month 2 of year 5. The investigators therefore anticipate recruiting 9 new dyads per month at all sites throughout the 4 years, with 5-6 through the VNA Health Group, 2-3 at the University of Utah and 1-2 at University of Miami.

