## 8 Assessment of Safety

- 8.1 This study is a minimal risk study given that it is an evidence-based implementation science intervention. However, the investigators will monitor for the following safety parameters and events throughout this study. In instances where an adverse event (AE) or a serious adverse event (SAE) has been identified, the investigators will follow standard clinical practice (SCP) whereby the investigator will notify the subject's health care provider responsible for initiating and/or approving the subject's enrollment into HHC services. In situations where an AE or SAE has been determined to be related to the study and the subject has withdrawn, investigators will actively monitor in follow up. Specification of Safety Parameters

CONFIDENTIAL

This material is the property of the NYU School of Medicine and Langone Medical Center. Do not disclose or use except as authorized in writing by the study sponsor  
 Interventional Template Version: 28 APR 2017

Due to the pragmatic nature of the trial, the DSMB has directed this trial to perform a highly focused AE collection process which requires following single adverse event: a PHQ-9 score worsened by greater than or equal to 5 points during the course of the study. The DSMB further requires monitoring the following severe AEs: Caregiver attempted suicide; death of caregiver; death of person with dementia a; medical event that may jeopardize the subject, including hospitalization of either the person with dementia or caregiver, suicidal ideation, elder neglect or abuse, or an environmental threat such as unsecured firearm.

In cases of the following safety parameters, the site-PI and PI shall be notified immediately, a telephone triage performed, and then SCP will be followed by notifying the subject's primary care provider to advise of the situation.

Due to the virtual nature of data collection, safety monitoring will be done to the best of abilities for:

- Imminent home safety threats/hazards (e.g. hoarding/cluttering, unsecured gun).**
- Suspected elder abuse or neglect.**

**Caregiver Depression:** Should caregivers have a score of  $\geq 10$  on the PHQ-9 or exhibit suicidal ideation via item 9 of the PHQ-9 or verbally outside of any instrumentation, Definition of Adverse Events (AE)

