**CONFIDENTIAL**

This material is the property of the NYU School of Medicine and Langone Medical Center. Do not disclose or use except as  
authorized in writing by the study sponsor

Caregiver attempted suicide: A case in which a caregiver is noted to have attempted suicide. This information may be provided by the PWD surrogate, PWD (if only mild dementia) or other family member, friend, or caregiver when attempting to complete follow-up visits.

Death of Caregiver: A case in which a caregiver is noted to have died. This information may be provided by the PWD surrogate, PWD (if only mild dementia) or other family member, friend, or caregiver when attempting to complete follow-up visits. We will attempt to ascertain the cause of death of the caregiver

Death of PWD: A case in which the PWD has died. We will attempt to contact the caregiver and primary care provider to ascertain the cause of death.

Any SAE will be immediately reported to the site-PI and overall PI, who will follow SCP by notifying the subject's health care provider and then notifying the IRB of record and DSMB for further review.

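### For dyads that fall silent, Section 7.2.7 names only the PWD's home health record as the safety source, and that record is not designed to capture the monitored caregiver events.

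*Combined protocol and SAP*

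**What the plan says.** Section 7.2.7 covers withdrawal. Staff will try to learn the reason and will "ask if any SAE or AE have occurred if the PWD/caregiver are reachable". For dyads that have stopped responding it adds one source: "if withdrawal is for non-communication with the study team we will review the HHC medical record to ascertain if there was an SAE or AE". Section 7.2.6 makes plain whose record this is: after the last visit "the home health agency will extract the PWD subject's health record".

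Section 8.1 lists the serious events that the DSMB requires to be followed, among them "Caregiver attempted suicide; death of caregiver", and also hospitalization of either dyad member. The single monitored non-serious event is a worsening of 5 or more points on the caregiver's PHQ-9.

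Section 8.1.1 defines the caregiver events by what comes to notice: "Death of Caregiver: A case in which a caregiver is noted to have died". The information may come from the PWD's surrogate, a PWD with mild dementia, "or other family member, friend, or caregiver when attempting to complete follow-up visits".

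Two sets of contact details are already held. Section 5.4 says that "Study staff will obtain detailed contact information for the PWD, caregiver, and where applicable proxy", and the baseline visit in 7.2.2 collects "primary care provider name and contact for both PWD and caregiver". Section 5.7.2 terminates both members if the caregiver does not complete visit 4.

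**The concern.** The text offers the record review as a way to find out whether an event occurred, but for the caregiver it looks in someone else's chart. A home health nurse may note a caregiver's death or hospitalization in passing; nothing makes the chart a source for it.

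The loss is also unlikely to be unrelated to the events. A caregiver who has died or is incapacitated cannot complete visit 4, so the dyad is terminated and, if nobody answers, falls under the weakest check. At stake is the completeness of the caregiver event tables that the DSMB sees. With few events expected, one missed death or suicide attempt matters, and a table that does not show how many caregivers were ascertained cannot be read correctly.

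**Working it through.** **1. Sources and events side by side, for a dyad withdrawn for non-communication**

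| Monitored event | Home health record (7.2.7) | Other route in the protocol |
|---|---|---|
| PWD death or hospitalization | Plausible source: the PWD is the agency's patient | Caregiver and primary care provider are contacted for the cause of a PWD death (8.1.1) |
| Caregiver death | Incidental mention only | Informant may report it during visit attempts (8.1.1); no contact is named for the cause |
| Caregiver suicide attempt | Incidental mention only | Same passive route |
| Caregiver PHQ-9 worsening | None: needs a second score | PHQ-9 is given only at days 0 and 60 (7.2.2, 7.2.5, Table 2), so a caregiver lost before visit 4 has no second score |

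The informant route is passive and gives nothing if nobody answers. No section requires a call to an alternate contact or to the caregiver's provider when a dyad goes silent. Section 13.4 does ask for an attempt to obtain permission to collect vital status at the end of the scheduled period, but only for subjects who revoke authorization. No section says how to record a caregiver whose status is unknown, although 10.3 keeps separate caregiver AE and SAE data sets.

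**2. Size of the group**

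Inputs: 300 completed dyads, 15% non-completion and 345 enrolled (5.6, 5.7.2, 10.5).

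- The plan's figure is reproduced: 300 × 1.15 = 345.
- Planned non-completers: 345 − 300 = 45, and 45/345 = 13.0%.
- Read literally, 15% of enrolled: 0.15 × 345 = 51.75, about 52.

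The range 45 to 52 covers every reason for non-completion. It is a ceiling for lost contact at the planned attrition.

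**3. What could be missed**

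The protocol gives no caregiver event rate, so the risks p below are assumptions for a caregiver death or suicide attempt. With m lost caregivers, the expected number is m × p and the chance of at least one is 1 − (1 − p)^m.

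| Assumed p | Expected events, m = 45 to 52 | Chance of at least one |
|---|---|---|
| 0.5% | 0.2 to 0.3 | 20% to 23% |
| 1% | about 0.5 | 36% to 41% |
| 2% | 0.9 to 1.0 | 60% to 65% |
| 5% | 2.3 to 2.6 | 90% to 93% |

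These rows apply the ceiling and assume that loss is unrelated to the event. If the event causes the silence, the risk among the lost is higher than in caregivers generally.

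**4. Effect of the denominator**

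Suppose no caregiver event is seen. The one-sided 95% upper bound is 1 − 0.05^(1/n).

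- n = 300 ascertained: 0.99%.
- n = 345, with all lost caregivers counted as event-free: 0.86%.

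The second figure would claim precision that the data do not have. The protocol does not say which denominator will be used.

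**The case against.** The strongest reply is that the record is not the sole safeguard. Section 8.1.1 names surrogates, family, friends and other caregivers as informants for these caregiver events. Separate contact details are held for the PWD, the caregiver and, where applicable, a proxy, with calls before each follow-up. Events are also asked about at visits 2 and 3, so a dyad lost later is covered up to its last contact. This stands: a reader might infer that the record is the only safety check, and that would be wrong. It is the only source that 7.2.7 names for silent dyads; the informant route exists but is not an active step.

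Three further readings are tempting and not supported.

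- That lost caregivers will be counted as event-free: the protocol gives no rule either way.
- That the halting decision rests on this count: Section 8.7 acts on a 20% or greater negative effect on a primary outcome, on SAEs caused by the program, or at discretion. Only the discretionary limb could draw on caregiver counts. Differential loss by arm is possible but not documented.
- That the record closes early: 5.4 expects home care usually to last at least 60 days.

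It is also fair to say that this is a minimal-risk trial for which the DSMB chose narrow event collection, that re-hospitalization and institutionalization are named as the greatest retention risks, and that the separately stored Study Manual (Section 18) may contain lost-contact steps. The proxy may be absent, or may be the caregiver. These points limit the size of the gap and the yield of the fix; they do not make the PWD's chart a source for caregiver events.

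**Conclusion.** The point holds as a modest, inexpensive improvement. For dyads withdrawn for non-communication, 7.2.7 relies on a record that is not designed to capture caregiver death, caregiver suicide attempt or PHQ-9 worsening, and the protocol requires no active alternate contact. Caregiver events may be undercounted in this group because the event can produce the silence.

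At most 45 to 52 of 345 caregivers are affected if attrition is as planned; the true number is smaller by an unknown share. At that ceiling and an assumed 1% risk, about half an event is expected among them. The conclusion rests on the protocol text alone, since the Study Manual is not part of it. Sample size, power and alpha are unaffected.

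**What to change.** In 7.2.7, for non-communication, add wording such as: *Staff will also attempt to reach the proxy or other alternate contact where one was recorded at enrolment and, where consent and HIPAA authorization cover it, the primary care provider collected at visit 1, to establish vital status and any monitored SAE for each dyad member.*

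Add a recording rule: *If only the home health record could be reviewed, the caregiver's safety status is coded as not ascertained after last contact.* In the DSMB reports (8.8.2), show caregiver events by arm with the number ascertained as denominator and the number not ascertained beside it. PHQ-9 worsening cannot be recovered by such a call and should be shown as not ascertained where there is no second score.

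The cost is one or two calls by existing staff per lost dyad, using details already collected, one extra status code, and a check of the consent and HIPAA wording before any call to the caregiver's provider. Some statuses will remain unknown; the code and denominator make that visible.
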